#### **Biochemical Measurements:**

Plasma for inflammatory markers, TRP, and TRP metabolites will be obtained at mid-week prior to dialysis on weeks 1, 4, and 12. Blood fluoxetine and hydroxyl-bupropion levels will be obtained at weeks 4, and 12. When possible, samples will be taken from pre-filtered blood at the dialysis site and sent to a research laboratory core at UAMS and/or UT San Antonio for analysis. Twenty ml of venous blood will be collected as described in Table 1. Blood for free- and total-TRP and large neutral amino acids (LNAA) will be assayed by high performance liquid chromatography with coulometric detection (HPLC) [105] and expressed in µM. Plasma KYN concentrations will be determined by HPLC [106]. Quinolinic acid will be quantified by electron capture negative chemical ionization gas chromatography/mass spectrometry with [180] QUIN as internal standard [107]. Determinations of plasma concentrations of CRP, IL-1β, IL-6, and TNF-α will be performed by ELISA with the use of Quantikine High Sensitivity kits (intra-assay coefficient of variation for these cytokines 2.0 to 8.6%; interassay coefficient of variation 3.9 to 7.0%; R&D Systems, Minneapolis, MN) following established guidelines [108]. Bupropion and its active metabolites hydroxybupropion and fluoxetine and norfluoxetine will be analyzed using HPLC and mass spectrometry (MS) [109] [110].

# The following tools will be utilized:

- a) The Mini International Neuropsychiatric Interview (MINI) [75]. Psychiatric diagnosis will be assessed with the MINI, a widely used semi-structured interview for DSM-IV diagnoses. It has high reliability, for MDD and depressive subtypes. (Time - 30 min).
- b) The Hamilton Depression (HAM-D) Scale [76]. Depressive symptoms in all phases of this study will be measured with the 25-item version of the HAM-D. (Time – 5 minutes).
- c) The Profile of Mood States (POMS) [81, 82]. The POMS is one of the most validated measures for measuring a wide range of clinical and subclinical changes in mood. It has been studied extensively in various clinical samples including psychiatric patients as well as in cancer, drug abuse and addictions, and the broad domain of exercise, fitness, sports psychology, and sports medicine. (Time – 10 min).
- d) The Brief Fatigue Inventory (BFI) [83]: It is used to assess the severity of fatigue and the interference of fatigue with daily functioning. The interference items include general activity, mood, walking ability, normal work (includes both work outside the home and housework), relations with other people, and enjoyment of life. The interference items are measured on a 0-10 scale, with 0 being "does not interfere" and 10 being "completely interferes." (Time – 5 minutes).
- e) The Modified Mini Mental Status (3MS) Examination [78]: The 3MS Examination is a validated screening tool to evaluate global cognitive function with components for orientation to time and place. attention, language, immediate recall, short-term verbal memory, calculation, construct ability, and memory. [84]. (Time – 8 minutes).

Version #: 17. IRB #203076

PI: [name]

f) Delay discounting task. It is a decision making task. Subjects will be presented a series of trials in which they will choose between a set of hypothetical rewards or losses to be received in variable time spans. Smaller sooner (SS) hypothetical reward/loss (\$X) received today or a larger later reward/loss (LL) (\$1000) received at a future delay (1wk, 1mo, 6mo, 1yr). The value of the SS award will be titrated with participant responses so that an equal number of SS and LL choices are selected for each delay. Time - 5 minutes [144].

g) Multi-Source
Interference Test
(MSIT): MSIT is a nonverbal test of attentional
conflict which combines
elements of the Stroop,

Table 1. Study Procedures									
Measures	Week of Study								

- Medication Accountability Record (Time 2-3 minutes). Used to record medication adherence.
   Pharmacy staff will record number of pills missing from previous week's bottle after each study visit.
- m) Physical and Psychological Pain Scale, self-report has 7 items and takes 2-3 minutes to complete. It characterizes psychological pain in comparison with physical pain [142].

PI: [name]

n) Pressure Pain Test Patients will be placed supine. A point five inches below the patella in the medial border of the tibia will be identified in both sides. Pressure will be applied using a digital force gauge with a 1-cm² rubber tip (J-Tech Medical, Commander Algometer or equivalent) alternately to the left and the right tibia for a total of three times each. Participants are instructed to verbally report when their sensations change from pressure to pain. A mean tender point threshold (kg) is calculated from the six measurements [143]. To prevent any possible tissue damage, stimulation will only be applied to a maximum of 20 Lb.

o) Quantitative Sensory Testing (QST) on untreated skin will be performed using cutaneous hot and cold stimuli via a thermal stimulator (Q-Sense) thermode on the Medoc Pathway System (Medoc Ltd Advanced Medical Systems, Ramat Yishai, Israel). It will be performed via method of limits testing on the right thenar eminence with a program designed to randomly order 5 hot and 5 cold stimuli with random durations (5–35 seconds) between each trial. The Q-Sense thermode will begin at 32°C and increase or decrease by 0.5°C per second. Participants will be instructed to press a button to signify 3 different measures: 1) sensory threshold, or the temperature at which the stimulus becomes noticeable; 2) pain threshold, or the temperature at which the stimulus becomes painful; and 3) pain tolerance, or the temperature at which the stimulus becomes unbearable. The device will be set to stop heating at 51.5°C and stop cooling at 0°C to avoid tissue damage.

#### Concomitant Clinical Management and Study Termination

Patients will continue to be managed by their treating physician during the study. Acute events that may require hospitalization are expected in this population. These events and possible interruptions of study drugs will be recorded, and if necessary, patients may be discontinued from the study. Patients expressing suicidal ideation or plans will be brought to the attention of the treating physician and treatment options discussed. The PI will be available for consultation on such cases. Depending on the severity and/or wishes of the treating physician and patient, a number of options are available, including transportation to a nearby emergency department, referral to the Psychiatry outpatient clinic, or medical intervention at the dialysis center.

Subjects may terminate the study at any time for any reason. Reasons for early discontinuation will be ascertained by research staff as best possible and recorded in the following categories: 1) unspecified patient request or failure to return, 2) patient request or physician decision due to clinical worsening without meeting relapse criteria: 3) adverse event, 4) protocol violation. Subjects that discontinue prematurely will be given referral options and advice, if possible.

Non-responders to treatment will meet with a physician to review options, including referral to a community clinic or the Psychiatry Department. Subjects that complete the study with no relapse will be given the option to be referred to a physician in the Psychiatry Outpatient Clinic or have their medication managed by their current general physician.

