# 3. Study Design

The current study proposes to randomly assign 40 CKD patients with MDD to 12 weeks of open label, flexible dose treatment with either bupropion (N=20) or fluoxetine (N=20).

[NOTE: We are requesting to enroll up to 50 subjects/with 40 completers. One of the outcome measures will be the number of weeks of treatment that a person completes. This is a preliminary feasibility and pilot study, so establishing an estimate of drop out rate will be important for when we design the "definitive" study in the future.]

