Tolerability and Safety: We will determine incidence rates for all adverse events and treatment emergent adverse events will be determined using the SAFTEE. Treatment emergent adverse events will be defined as those that were not present before the first administration of drug, but occurred after the first administration, or that were present before the first administration but increased in severity or frequency after the first administration. Incidence rates for all adverse event and treatment emergent adverse events will be compared between medication groups using chi-square for frequencies with any events or Poisson regression for counts of numbers of events adjusting for time at risk using log time as an offset variable. The numbers of subjects withdrawing from the study for each reason will also be compared across groups using survival analysis on time to study discontinuation.

Version #: 17, IRB #203076

PI: [name]

**Testing Hypothesis 1**. Both antidepressants will be efficacious based on change in Ham-D scores over time. The primary analyses will be mixed effects regression models with repeated measures (baseline, 1, 4, 8, 12 weeks) performed separately in the medication groups. The fixed effect is time, and the hypothesis test is an *a priori* contrast comparing the baseline value with the average of the four post-baseline values. In secondary analyses, patients will be categorized as responders and remitters, with response defined as a 50% or greater improvement in Ham-D score with total score ≤ 15 at the 12 weeks compared with baseline and remission [129] as having had a treatment response plus a final Ham-D score ≤7.

**Testing Hypothesis 2**. Changes in cognition, fatigue, and depression will be evaluated between and within treatment groups. Changes in BFI and cognition should be greater in bupropion SR-treated patients [30, 32, 89, 130-140]. These analyses will use mixed effects regression models with repeated measures. Treatment group, time and their interaction are the fixed independent variables. Change in Ham-D, BFI and cognitive dysfunction (3MS, MSIT, and n-back performance) are the time-varying dependent variables. All subscales of the BFI will be summarized by time point.

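### The closed list of withdrawal reasons ties its only efficacy category to undefined relapse criteria and has none for lack of improvement, so the by-reason results cannot reliably separate efficacy failure from intolerance.

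*Combined protocol and SAP*

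**What the plan says.** All of the following is in the combined protocol and SAP.

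- **Concomitant Clinical Management and Study Termination** sets the recording rule: "Reasons for early discontinuation will be ascertained by research staff as best possible and recorded in the following categories". The first category is a patient request with no specified reason, or not coming back. The second is "patient request or physician decision due to clinical worsening without meeting relapse criteria". The third is adverse event and the fourth is protocol violation. No category for other reasons follows.
- The last paragraph of that section uses the term once more: "Subjects that complete the study with no relapse will be given the option to be referred". It gives no definition.
- **Data Analysis, Testing of Hypothesis 1** defines two outcome states. Response: "response defined as a 50% or greater improvement in Ham-D score with total score ≤ 15 at the 12 weeks". Remission: "as having had a treatment response plus a final Ham-D score ≤7". Testing Hypothesis 3 adds residual symptoms (HAM-D above 15). None of these is a relapse criterion.
- **Data Analysis, General Methods** plans a disposition table that counts drop-outs by reason.
- **Data Analysis, Tolerability and Safety** plans a comparison between drugs: "The numbers of subjects withdrawing from the study for each reason will also be compared across groups", by survival analysis of time to discontinuation.

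**The concern.** A comparison by reason needs categories that are exhaustive, mutually exclusive and applied alike in both arms. This list falls short in two places. Its one efficacy category carries a qualifier that nobody can apply, because the criterion does not exist. It also offers nothing for a patient who leaves because the drug has not helped.

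At stake is the split between efficacy failure and intolerance. The Tolerability and Safety analysis compares drugs on that split, and it is part of what a pilot hands to the team designing the definitive trial. Treatment is open label according to Study Design and Research Plan, and the second category includes decisions by a physician. An undefined boundary could therefore be drawn differently for the two drugs. The rater blind to medication in the Research Plan is assigned ratings such as the Ham-D. Reasons for leaving are ascertained by research staff, and the protocol does not say that those staff are blind.

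**Working it through.** No sample size, power or alpha figure depends on these categories, so there is no stated figure to reproduce. The check is textual.

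**Step 1: is relapse defined?** Outside the titles in the reference list, the word occurs twice in the study text, both times in Concomitant Clinical Management and Study Termination, and neither time with a threshold. Nor can a threshold be inferred from the design. Patients enter in a current episode (DSM-IV major depression and Ham-D above 17), and the only defined states are response, remission and residual symptoms.

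**Step 2: where does each kind of withdrawal go?**

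| Reason for leaving | Category that fits as written |
|---|---|
| Mild worsening | 2 |
| Marked worsening | 2, if no one can meet absent criteria; or 3, because the treatment-emergent definition in Tolerability and Safety includes pre-existing conditions that become more severe |
| No improvement, no worsening | None; falls to 1 or to a wrong reason |
| Death or acute medical event unrelated to drug | 3 |
| Adverse drug effect | 3 |

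Two rows are defective: marked worsening has two defensible codes, and lack of improvement has none. The fourth row is not a gap. Category 3 does not require drug-relatedness, the adverse-event section requires any change in health from baseline to be reported, and the DSM Plan names death and hospitalization as serious adverse events.

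**Step 3: which outputs use the codes?** The by-reason disposition table and the by-reason comparison between drugs do. The total count, the weeks of treatment completed and the overall time to discontinuation do not.

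**Step 4: size.** Study Design and Research Plan allow up to 50 enrolled for 40 completers. That gives 50 − 40 = 10 withdrawals at the ceiling, and 1/10 = 10% of withdrawals per misfiled patient.

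To illustrate, assume that 3 of the 10 leave for marked worsening. Category 2 then receives anywhere from 0 to 3 of them, depending on the coder, and the total stays at 10. The documents give that range and no point within it.

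**The case against.** The strongest reply starts from the missing definition itself. If relapse criteria do not exist, nobody can meet them, and category 2 takes all worsening, mild or severe. This stands against one tempting inference, that the most severe loss of efficacy has no category and that a worsening count of 3 would be reported as 0. That result needs staff to apply a criterion the documents do not contain. It does not rescue the list, because the protocol nowhere tells staff to read it this way, coding as an adverse event is equally defensible, and lack of improvement still has no home.

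A reader might also infer that deaths and intercurrent illness fall outside the list. As shown above, they fit under adverse event. Relatedness is judged separately by the clinician in the SAFTEE.

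A third inference would be that the pilot's drop-out estimate is biased. Study Design says that "establishing an estimate of drop out rate will be important", but that is the overall rate, which does not change with the reason code.

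Finally, the numbers are small. Assume 25 patients per arm and all 3 worsening withdrawals in one arm. Two-sided Fisher p is then 2 × C(25,3)/C(50,3) = 2 × 2300/19600 = 0.23. The plan names survival analysis rather than this test, but the message is the same: by-reason results will be descriptive under either coding. Ham-D and CGI are collected throughout, and source narratives may allow recoding later. These points limit the consequence. They do not justify leaving a known ambiguity in a list that two planned outputs use.

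**Conclusion.** The point holds as a defect in how withdrawal reasons are recorded. Followed as written, the list misfiles withdrawals for lack of improvement and leaves marked worsening open to two codes, so the by-reason table and the by-reason drug comparison cannot be relied on to separate efficacy failure from intolerance. Each affected patient is 10% of the withdrawals, assuming 50 enrolled and 40 completing. How many patients would be affected, and in which direction, cannot be derived from the documents. The conclusion also rests on the list being closed, as its wording indicates, and on treatment being open label; General Methods calls the assignment double-blind, at odds with Study Design and Research Plan. If coding were in fact blind, differential coding by arm would be less likely, but the gap in the list would remain.

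This is worth correcting because it is cheap. It does not threaten the efficacy analyses or the overall drop-out estimate.

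**What to change.** In the list of discontinuation reasons:

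1. Remove the relapse qualifier from category 2, so that it covers clinical worsening of any degree.
2. Add an explicit reason for lack of improvement, recorded separately from worsening. State in advance that the two may be pooled for analysis if numbers are small.
3. Leave deaths and intercurrent events under adverse event, and use the relatedness judgement already collected to separate them from drug intolerance in the table.

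The undefined term also appears in the last paragraph of the same section, where it bears on referral and continued medication management. That is clinical management, so the request there is only that the sponsor reconcile it with the rest of the protocol. None of this sets a stopping rule.

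The cost is one protocol line and one case-report-form list. The downside is slightly sparser categories among about 10 planned withdrawals.

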# **End of study Follow-up Phone call**

Participants will be contacted by phone at week 14 (two weeks after concluding the trial) to determine if the participant is experiencing any post-treatment adverse events related to the cessation of study medications. Participants experiencing distress will be referred to the UAMS Walker Family Clinic for further psychiatric care.

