Participants will receive the study medication during the baseline assessment and instructed to begin the medication on day 1 (1st dialysis day) of week 1 of the study. For patient on hemodialysis or peritoneal dialysis, generic bupropion SR will be dosed at 150 mg on the 1st and the 3rd dialysis day of each week with doses adjusted upward or downward based on tolerability. The initial dose of bupropion-SR is based on the findings of Worrall et al [80], who measured plasma bupropion levels in a pharmacokinetic study of bupropion in HD patients. For patient not on hemodialysis or peritoneal dialysis, generic bupropion SR tablet will be dosed at 150 mg daily. Bupropion SR doses will be adjusted upward or downward based on tolerability and response. Fluoxetine will be started at 10 mg/day for the first week and then increased, as tolerated to 20 mg/day for weeks 2–4. After this, doses will be adjusted based on clinical response and side effects up to a maximum dose of 60 mg/daily by week 10 [62]. At the week 12 visit, the participants will stop the medication or may undergo a 1-2 week taper (depending on maintenance dose) if they are on a dose of fluoxetine that is higher than 20 mg.

Subjects will be seen during weeks 1, 2, 3, 4, 6, 8, 10, and 12 in face-to-face meetings by a rater blind to study medication and a study physician for Ham-D ratings, CGI, medication accountability, and measurement of adverse events. On weeks 5, 7, 9 and 11, subjects will come in to return the previous week's pill bottles and pick up the current week's medication. Table 1 shows study procedures. Medication will be prepared by UAMS Research Pharmacy, labeled with the directions for use and contact information, and given to participants by study staff on a weekly basis. Compliance will be monitored using the MAFV at each scheduled encounter and by analysis of antidepressant blood levels. Results of a second EKG done during week 4 will be reviewed to ensure QTc interval is less than 500 msec.

In order to control for the potential confound of chronic pain we will characterize it with the physical and psychological pain scale and with two objective measures, i.e. the pressure pain threshold and the Quantitative Sensory Test (QST).

Version #: 17, IRB #203076

PI: [name]

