Rare These risks are expected to occur in less than 2 subjects out of 100			
 
Suicidal ideation
 
Suicide
 
Serotonin syndrome symptoms (mental status changes [agitation], increased heart beat, change in blood pressure, dizziness, tremor, seizures, and/or nausea, vomiting, diarrhea)
 
Allergic reactions (Anaphylactoid reactions - including bronchospasm, angioedema, laryngospasm, and urticarial) and skin rash
 
				

Risks associated with stopping the study medication. To our knowledge, there are no known risks to stopping bupropion abruptly. In addition, although abrupt termination of selective serotonin reuptake inhibitors (SSRIs) have been associated with a SSRI discontinuation syndrome (consisting of symptoms described as "head shocks," dizziness, electric shock-like sensations, sweating, nausea, insomnia, tremor, confusion, nightmares, and vertigo), fluoxetine has been associated with only mild dizziness and vertigo in patients maintained on fluoxetine at 20 mg/day that was abruptly terminated in a randomized double blind trial (141).

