#### **Procedures to Minimize Risks**

- All side effects will be closely monitored;
- Physical examination and blood test results will be performed reviewed to help detect an increased risk of developing side effects;
- Aseptic precautions to minimize risks associated with blood draw;
- Subjects will be educated to share any unusual event or change in their health with the study staff;
- Study staff will ask questions to elicit any new event or change in their health during each encounter;
- The study procedures to be performed on subjects are consistent with sound research design.
- Participants maintained on fluoxetine at doses higher than 20 mg/day will undergo a 1-2 weeks taper depending on the maintenance dose.
- The researchers have taken steps to minimize the known or expected risks. However, appropriate medical treatment will be provided for any adverse event (anticipated or un-anticipated) as per standard medical practice and guidelines. In addition, the event will be documented for proper notification. In addition, following measures will be implemented:
  - All patients will continue to be managed by their treating physician during the study. Acute events that may require hospitalization for reasons unrelated to the study are possible in this population. These events and possible interruptions of study drugs will be recorded, and if necessary, patients may be discontinued from the study. Patients expressing suicidal ideation or plans will be brought to the attention of the treating physician and treatment options discussed. The PI will be available for consultation on such cases. Depending on the severity and/or wishes of the treating

Version #: 17, IRB #203076

PI: [name]

physician and patient, a number of options are available, including transportation to an emergency department medical facility, referral to Psychiatry outpatient clinic, or medical intervention at a nearby dialysis center.

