#### Costs to Subjects.

The Investigator will provide the study drug free of charge during this study. In addition, all tests, examinations, and medical care required in this study are provided to a participant at no cost. There will be no costs for the subject participation

The researchers will take steps to minimize the known or expected risks. However, the subject may still experience problems or side effects, even though the researchers are careful to avoid them. If the subject believes that he/she has been harmed, she/he will be instructed to notify the researchers as soon

Version #: 17, IRB #203076

PI: [name]

as possible. In the event of a research-related injury or if the subject experiences an adverse reaction, he/she will be instructed to immediately contact the study doctor.

If the subject is injured as a result of the research procedures, the injury will be treated.

The subject/insurance company will be responsible for any charges. We have no plans to give the subject money if he/she is injured.

Subjects are informed that they do not give up any of legal rights by signing the Consent Form.

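### The only post-treatment safety call is fixed at week 14, so a fluoxetine patient on a 2-week taper has had about 0 drug-free days when it is made, and no later contact is scheduled

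*Combined protocol and SAP*

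**What the plan says.** Under *End of study Follow-up Phone call* the combined protocol and SAP sets the timing: "Participants will be contacted by phone at week 14 (two weeks after concluding the trial"). The call is to establish whether the participant is "experiencing any post-treatment adverse events related to the cessation of study medications".

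Treatment does not end at the same time for everyone. Section 6, *Research Plan*, says that at week 12 "the participants will stop the medication or may undergo a 1-2 week taper", the taper applying to fluoxetine above 20 mg. *Procedures to Minimize Risks* puts it more firmly: "Participants maintained on fluoxetine at doses higher than 20 mg/day will undergo a 1-2 weeks taper depending on the maintenance dose". Such doses are foreseen, because after week 4 fluoxetine is "adjusted based on clinical response and side effects up to a maximum dose of 60 mg/daily by week 10".

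The Table 1 schedule, including the SAFTEE adverse event interview, ends at week 12. After the week 14 call the document schedules no further study contact.

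**The concern.** The call exists to detect the effects of stopping, but its date counts from the week 12 visit and not from the last dose. For a patient still tapering after week 12, the two differ by the length of the taper.

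The patients affected are those on the higher fluoxetine doses. The protocol's reassurance about withdrawal, in the paragraph on stopping study medication under *Risks and Benefits*, comes from a lower dose: "fluoxetine has been associated with only mild dizziness and vertigo in patients maintained on fluoxetine at 20 mg/day that was abruptly terminated". So the patients whom the protocol singles out for a gradual stop get the shortest drug-free observation. Observation after treatment is also uneven between the arms, since no bupropion taper is planned.

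At stake is the detection of withdrawal problems that start only after the last taper dose. Without a scheduled enquiry, these come to light only if the patient reports them or later clinical care passes them on.

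**Working it through.** **Inputs**
- End of full-dose treatment: the week 12 visit (section 6, *Research Plan*).
- Taper length: 0 weeks for bupropion and for fluoxetine up to 20 mg/day; 1-2 weeks for fluoxetine above 20 mg/day (section 6 and *Procedures to Minimize Risks*).
- Call: week 14 (*End of study Follow-up Phone call*).

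**The plan's own figure.** The call is described as two weeks after the trial concludes: 12 + 2 = 14. This reproduces the stated week and shows that the count runs from the week 12 visit, not from the end of a taper.

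**Drug-free days at the call**, as (14 − 12 − taper weeks) × 7:

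| Taper | Last dose | Calculation | Drug-free days at week 14 |
|---|---|---|---|
| None | week 12 | (14 − 12 − 0) × 7 | 14 |
| 1 week | week 13 | (14 − 12 − 1) × 7 | 7 |
| 2 weeks | week 14 | (14 − 12 − 2) × 7 | 0 |

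**If the call were set at last dose + 2 weeks**, it would fall at:
- no taper: 12 + 0 + 2 = week 14
- 1-week taper: 12 + 1 + 2 = week 15
- 2-week taper: 12 + 2 + 2 = week 16

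Each gives 2 × 7 = 14 drug-free days.

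**Does anything else scheduled cover the gap?**
- Table 1, with SAFTEE, stops at week 12.
- The adverse event section has the team follow every event until it resolves satisfactorily, but this works only for events already known to the study.
- Under *Costs to Subjects*, a patient with an adverse reaction is told what to do: "he/she will be instructed to immediately contact the study doctor". That depends on the patient.
- Under *Concomitant Clinical Management and Study Termination*, completers without relapse may be referred to psychiatry or "have their medication managed by their current general physician". That is clinical care, not a study safety contact.

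None of these is a planned enquiry after the end of a 2-week taper.

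**The case against.** The strongest case on the other side accepts the arithmetic and disputes the consequence.

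- **Follow-up to resolution.** A symptom that starts during dose reduction and is reported at week 14 must be followed further. This stands. It narrows the gap to patients who are well at the call, develop symptoms only after the last dose, and do not report them. It does not close it.
- **Continuing care.** Non-responders meet a physician, and some completers may go on with medication under their own doctor, so that drug-free time does not arise for them. This also stands, but it does not help those who taper and then stop.
- **Harm not shown.** The document gives no onset time for withdrawal symptoms and no evidence on symptoms after a completed taper; the taper is itself the safeguard. Nor does it show that 14 days is the right interval, which is simply what untapered patients receive. This is fair. What remains is a mismatch between the call's stated purpose and its timing, not a demonstrated harm.
- **Few patients.** Only those given the full 2 weeks reach 0 days, and that could be none. The number is indeed unknown.
- **Moving the call has a price.** Tapered patients would have no scheduled safety enquiry for 3-4 weeks after week 12, in a depressed population for whom suicidal ideation is listed as a rare risk. This is a real trade-off, and it is the reason to consider the alternative given under the fix.

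**Conclusion.** The concern holds. At the week 14 call, drug-free time is 14 days without a taper, about 7 after a 1-week taper and about 0 after a 2-week taper. In the last case the call cannot detect problems that begin after dosing ends, and nothing later is scheduled.

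The figures assume that the taper starts at the week 12 visit, runs its full length, and that the call is made in week 14 as written. The document does not say which doses get 1 week and which get 2, or how many patients will be above 20 mg/day, so the number affected can be given only as some part of the planned 20 fluoxetine patients.

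This is a minor, worthwhile improvement. It does not touch the efficacy analyses or the SAFTEE-based comparison of adverse events under *Tolerability and Safety*. Confidence is high in the timing and lower in how much it matters clinically.

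**What to change.** Under *End of study Follow-up Phone call*, set the call two weeks after the last dose of study-supplied medication, including any taper: week 14 for patients who stop at week 12, week 15 after a 1-week taper, week 16 after a 2-week taper. As a clerical matter, align section 6 (*may* taper) with *Procedures to Minimize Risks* (*will* taper), so that it is clear whether the taper above 20 mg/day is required.

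The cost is wording in two places, with no added call. The drawback is that tapered patients are asked about the taper period 3-4 weeks after week 12 instead of 2; until then the instruction to contact the study doctor applies. If the sponsor does not want to give up the week 14 check, it can keep that call for everyone and add a second one, two weeks after the last dose, for tapered patients only. That costs one extra call for each of them.
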